7.6 TEST MATERIALS

7.6.1 Administration

Study drug will be applied by the subject to the entire area of the face, once daily, in the morning, for a period of 12 weeks after performing the first application of study drug at the study site, under the

CONFIDENTIAL

Version Date: 31 March 2017

supervision of the study coordinator or designee to ensure the subject understands the treatment application instructions (see Appendix A, Instructions on Application of Study Drug). The subject will be provided a copy of the Instructions on Application of Study Drug. Once the subject has read the instructions and demonstrated proficiency in application at the study site, subjects will continue daily treatment application, each morning, during the treatment period in an outpatient setting.

Subjects will be instructed to wash their face with a non-medicated soap or soapless cleanser at least 15 minutes prior to application of the study drug. The study drug is packaged in a tube. The cap of the tube should be removed and a thin film coating of the gel should be applied to the entire face, avoiding contact with the eyes, mouth and inside the nose. The dose applied will be applied as a thin film, approximately 0.4 gram each day, preferably in the morning.

At the Baseline visit and Week 3, 6 and 9 visits, subjects will be dispensed one tube of study drug during the double-blind study period. Each tube contains enough gel for 4 weeks of treatment. During the open-label extension study period, subjects will be dispensed 2 tubes of study drug at Week 12 and 3 tubes of study drug at the Week 16, 26 and 39 visits. When the tube is dispensed and prior to application of study drug, the tube(s) will be dated and weighed and the weight will be recorded in the source documents and eCRF. When the used tubes are returned at the next visit, the tube will be weighed again, and the weight will be recorded in the source documents and the eCRF. At each visit, the subject's diary should be reviewed to determine if they missed any applications since the last visit. Reported missed applications should be recorded in the eCRF. In addition, the date of the last application should be collected. At each visit the returned tube(s) will be weighed to confirm product use. If necessary, the subject will be reinstructed on study drug application if compliance is an issue. All tube weighing will be done with the cap in place.

7.6.2 Products Identity

Omiganan Topical gel [REDACTED] in this protocol, in previously conducted phase 1 and 2 clinical studies, and in other historical documentation is based on the concentration of omiganan pentahydrochloride. The product concentration based on the active moiety is omiganan topical gel [REDACTED]. To be consistent with the naming convention in pre-existing documents, the nomenclature concentration of omiganan [REDACTED] will be referred to in this protocol and associated clinical and non-clinical documents.

[REDACTED]

Further, in order to comply with USP General Chapter <1121> Nomenclature to express the strength of the drug product based upon the active moiety, the strength of the omiganan product will be recorded on the clinical supplies documentation for phase 3 studies as Omiganan topical gel, [REDACTED]

CONFIDENTIAL

Version Date: 31 March 2017

Unblinding a subject, if needed, will be done through the IWRS. Unblinding a subject's treatment assignment should ONLY be performed in an emergency, when knowing the identity of a subject's assigned treatment is essential to their continuing medical care. If at all possible, every attempt should be made to contact the Medical Monitor to discuss this before unblinding to determine the subject's treatment assignment. The contact information for the Medical Monitor's is provided on the front page of the protocol. In the event of unblinding, the Medical Monitor and Project Manager must be notified immediately (within 24 hours (1 business day)), and the circumstances under which the code for a given subject was broken must be documented in the subject's eCRF.

During the safety extension portion of the study, the supplies will be open label and the label will indicate the contents of the tube.

7.6.5 Packaging

Study drug will be provided in 20-gram tubes. Drug supplies will be packaged to provide one treatment kit that contains 5 tubes of study drug per subject for the double-blind portion of the study. Four tubes will be provided in order to dispense a tube at Baseline, Weeks 3, 6 and 9. One extra tube will be in the kit in case tubes are lost or damaged. Each tube will be printed with the treatment kit number that will correlate through the randomization list to the contents of the tube.

The safety extension study supplies will be open-label bulk supplies. The subject will be dispensed omiganan topical gel in 20 gram tube(s) as appropriate (2 or 3 tubes). Additional tubes will be available to dispense to a subject in the event they are needed.

7.6.6 Labeling

The requirements for drug product labeling for double blind and open label supplies will comply with the regulations of the country where the clinical trial will be conducted.

Subjects will be provided a leaflet or card to keep with them at all times during the study that will provide the investigational site with the address and telephone number of the main contact for information on the product, clinical trial and for emergency unblinding.

Each double blind treatment kit (consisting of 5 tubes of study drug) will be labeled with language that adheres to the applicable regulatory requirements in each country.

Each double blind tube within the treatment kit will be labeled with labeling that corresponds to the treatment kit number. The study site personnel will write in the subject number and date of dispensing on the label when dispensing a tube. Tube labeling will contain language that adheres to the applicable regulatory requirements in each country.

Each open label tube will be labeled according to country regulations and will include the product identity.

CONFIDENTIAL

Version Date: 31 March 2017

7.6.7 Subject Dosing and Use Instructions

Under the supervision of the study coordinator or designee, the first dose of study drug will be applied by the subject, as a means of educating subjects in the proper technique for applying the study drug (see Appendix A for instruction on applying the drug). Once the subject has shown proficiency in application, subjects will then apply the dose each day preferably in the morning in an outpatient setting. During the open-label extension to the study, the dosing instructions will remain the same and subjects will be re-educated on treatment application, as needed.

7.6.8 Treatment Compliance

Subjects should not miss ANY visits to the study site for status assessments. Study drug treatment compliance will be assessed by reviewing the subject's diary for any missed applications since the last visit or based on subject reported information on missed applications in the event of a lost diary. Subjects should be applying the topical gel each day during the study treatment period.

7.6.9 Dispensing and Return of Study Product

For use in the outpatient setting, 1 tube of study drug will be dispensed to each subject from their assigned study drug supply kit at Baseline, and again at their Week 3, 6 and 9 visits during the double-blind portion of the study. The first dose of study drug will be applied at the study site. Subjects will be instructed on the proper procedure for study drug application for subsequent doses. Starting at the Week 12 visit, 2 to 3 tubes of open-label supplies will be provided at the Week 12, 16, and 39 visit and the subjects will be reminded of the instruction for treatment application.

When a new tube of study drug is dispensed, study personnel must record the date dispensed and subject number on the label. The dispensing information must be recorded in the source document.

The tube should be weighed prior to dispensing to the subject and again after the subject returns the tube to the clinical study site. The weight of the tube should be recorded to the nearest tenth of a gram. Tubes should be weighed with the cap on.

The subject will be instructed to return the supplies of study drug at each study visit to check compliance. During the double-blind portion of the study, at the Week 3, 6, and 9 Visit, the used tube will be exchanged for a new tube of study drug from the subject's kit. One extra tube will be available in each kit for dispensing in the event that tubes are lost or damaged during the double-blind portion of the study.

During the open-label safety extension period, tubes of study drug will be dispensed from a bulk supply and extra supplies will be available in the event that a tube(s) is (are) lost.

7.6.10 Accountability

In accordance with local country regulations, the Investigator must agree to keep all clinical supplies in a secure location with restricted access.

CONFIDENTIAL

Version Date: 31 March 2017

Upon receipt of the clinical supplies, the Investigator or designee will conduct a complete inventory of all test materials and assume responsibility for storage and dispensing. Dispensation and return of test material must be appropriately documented. Under no circumstance should any of the clinical supplies sent to the Investigator be used in any unauthorized manner.

All used and unused clinical supplies will be appropriately inventoried and returned to the designated facility as specified by the Sponsor.

7.6.11 Prior and Concomitant Medication/Therapy

Therapies used within one month prior to the Baseline visit should be recorded on the Previous/Concomitant Medication/Therapy Form of the CRF. Washout medications should be listed on the Previous/Concomitant Medication/Therapy Form, when applicable. Rosacea treatments used in the last 5 years should be recorded.

Any therapy used by the subject either at or following the Baseline visit through study completion will be considered concomitant therapy; e.g., aspirin, Tylenol, birth control pills, vitamins, etc. Every attempt should be made to keep concomitant therapy dosing constant during the study. Any change to concomitant therapy should be noted on the Previous/Concomitant Therapy page in the eCRF.

An Adverse Event should be recorded for any subject starting a concomitant therapy (except therapies used as prophylaxis) to treat any health condition/event not identified in the subject's medical history.

Subjects should wash their face 15 minutes prior to study drug application. Subjects must adhere to the following restrictions during the treatment period starting in the morning of Day 1:

- Showering/bathing (when subject showers/bathes, he or she should wait at least 15 minutes prior to applying study drug).
- Males should shave at the same time every day, at least 15 minutes before study drug application.
- Wait until the gel dries before applying makeup.
- Refrain from sunbathing, using sun tanning booths/beds, or excessive exposure to the sun.
- No new lotions, gels, powders, moisturizers, etc., are to be used on the skin in the treatment areas. A bland moisturizer may be used throughout the study. All makeup, approved lotions, moisturizers, etc. and sunscreen should be applied after the study gel is dry.

7.6.11.1 Excluded Concomitant Therapy

No other rosacea treatment, other than the study drug, will be permitted. Receiving interfering rosacea therapy during the study will be deemed a major protocol violation and may exclude the subject from the per protocol population for efficacy analyses. The medical monitor should be notified of deviations related to concomitant therapy. Interfering concomitant therapies include those listed below:

CONFIDENTIAL

Version Date: 31 March 2017

Interfering Topical Therapies (on the face)

- Abradants, astringents, toners, facials, masks, washes, or medicated facial cleansers
- Tanning booths/sunbathing, excessive exposure to the sun (tanning is not permitted)
- Antibiotics other than topical ocular application
- Antimicrobial soaps
- Corticosteroids
- Other anti-inflammatory drugs
- Retinoids
- Other acne or rosacea treatments (e.g., benzoyl peroxide, alphahydroxy acids, salicylic acid, azelaic acid, or metronidazole)

Interfering Systemic Therapies

- Antibiotics
- Corticosteroids other than inhaled/nasal corticosteroids
- Other acne or rosacea treatments (including oral retinoids or therapeutic vitamin A supplements)
- Change in dose, initiation and/or discontinuation of estrogen therapy (e.g., Gynogen, Valergen, Depo-Testadiol, Depogen, birth control pills)

7.7 STATISTICAL METHODS PLANNED

7.7.1 General Considerations

Unless otherwise specified, all statistical tests will be two-sided with a significance level of 0.05.

7.7.2 Sample Size Determination

The primary objective of the study is to show superiority of Omiganan over vehicle for the treatment of rosacea in patients with severe papulopustular rosacea (IGA grade 4 with baseline inflammatory lesion count ≥ 30). A sample size calculation was made for two co-primary endpoints. For change from baseline in inflammatory lesions, it is assumed that in the Omiganan treatment arm, subjects will have an average reduction of 13.5 inflammatory lesions, compared to 4 in the vehicle arm. The standard deviation is assumed to be 12. For 95% power, a sample size of 86 subjects (43 per group) is needed. For IGA, it is assumed that Clear or Almost Clear (IGA of 0 or 1) at Week 12 has lesser power than 2 grade (point) reduction. It is also assumed that 17% of the subjects in the omiganan treatment arm versus 6% in the vehicle arm will have an IGA of clear or almost clear at Week 12. For 95% power and using a Fisher's Exact test, 450 subjects (225 in each arm) are needed. Therefore, the number of subjects needed to ensure at least 95% power for both endpoints is 450.

The sample sizes were calculated using 95% power in order to ensure 90% power across two Phase 3 studies.

CONFIDENTIAL

Version Date: 31 March 2017

7.7.3 Randomization

Subjects providing written informed consent and having met all inclusion and exclusion criteria will be randomized to 1 of 2 treatment groups in a 1:1 ratio during the double-blind portion of the study, according to a predetermined computer-generated randomization code.

Subjects will be randomized to treatment using an Interactive Web Response System (IWRS). The randomization scheme will include investigative site. The randomization will be performed using permuted blocks.

7.7.4 Analysis Populations

The 'Intent-to-treat' (ITT) analysis population will include all randomized subjects. The ITT population will be the primary population for all efficacy analyses.

The "All-treated" analysis population will consist of all subjects receiving at least one application of study medication. All safety analyses will be performed on the all-treated population.

The Per-Protocol (PP) population will include all subjects in the ITT population who provide Baseline and Week 12 efficacy data for all primary endpoints and complete the 12-week treatment period without any major deviations from the protocol.

The subjects to be included in the PP analysis population will be determined by the Sponsor/CRO prior to the unblinding of the study. The PP population will be secondary for the co-primary endpoints only.

7.7.5 Handling of Missing Data

The primary method of dealing with missing data is multiple imputation (MI) technique. All co-primary and secondary endpoints will be analyzed using MI for missing data. As a sensitivity analysis, Observed Case and Baseline Observation Carried Forward (BOCF) will be utilized for the co-primary endpoints only.

In general, data will not be imputed for safety analysis.

7.7.6 Efficacy Endpoints

7.7.6.1 Co-primary Endpoints

- The absolute change from Baseline to Week 12 in inflammatory lesions.
- IGA at Week 12: 2 grade reduction; Clear or Almost Clear (IGA 0 or 1).

7.7.6.2 Secondary Endpoints

- The absolute change from baseline to Week 9 in inflammatory lesions (papules and pustules).

CONFIDENTIAL

Version Date: 31 March 2017

- The absolute change from baseline to Week 6 in inflammatory lesions (papules and pustules).
- IGA at Week 9: 2 point reduction; Clear or Almost Clear (IGA 0, 1).
- IGA at Week 6: 2 point reduction; Clear or Almost Clear (IGA 0, 1).

7.7.6.3 Exploratory Endpoints

- The absolute change from baseline to Weeks 1 and 3 in inflammatory lesions (papules and pustules).
- Percentage of subjects with an IGA of clear or almost clear (0 or 1) at Weeks 1 and 3.
- Percentage of subjects with a 2 point IGA reduction at Weeks 1 and 3.
- Percentage of subjects with an Investigators Assessment of Erythema (IAE) of clear or almost clear (0 or 1) at each visit.
- Percentage of subjects with telangiectasia score of none or mild (0 or 1) at each visit.
- Percentage of subjects with scaling/peeling score of none or mild (0 or 1) at each visit.
- Percentage of subjects with pruritus score of none or mild (0 or 1) at each visit.

7.7.7 Demographic and Baseline Characteristics

Continuous demographic and baseline parameters will be summarized by the number of non-missing observations, mean, standard deviation, median, minimum, and maximum. Categorical parameters will be summarized by frequencies and percentages.

7.7.8 Subject Disposition

Study completion status and reasons for discontinuation will be summarized by frequencies and percentages.

7.7.9 Study Product Exposure

The number of days of exposure will be summarized by the number of non-missing observations, mean, standard deviation, median, minimum, and maximum.

7.7.10 Efficacy Analysis

The co-primary endpoint of absolute change from baseline in inflammatory lesions will be analyzed using an Analysis of Covariance (ANCOVA) model, with treatment as a main effect, and center as a covariate. To investigate consistency of efficacy results across study centers, treatment by study center interaction will be tested at 0.10 level of significance, and if significant, it will be further explored.

The co-primary endpoint of IGA will be tested in the following manner: The 2 grade reduction, and the Clear or Almost Clear (0, 1) will be tested using the Hochberg procedure as follows: Statistical significance will be concluded if both endpoints are significant at a two-sided 0.05 level, or either endpoint is significant at a two-sided 0.025 level. Both IGA endpoints will be analyzed using a Cochran–Mantel–Haenszel (CMH) test, with center as the stratification factor. If the overall IGA

CONFIDENTIAL

Version Date: 31 March 2017

response rates are less than 10%, a Fisher's Exact test will be used to corroborate the CMH test. All tests of the co-primary endpoints will be analyzed.

If the co-primary endpoints of absolute lesion reduction and the two IGA endpoints (2 grade reduction, and Clear or Almost Clear (0, 1)) are both significant, the secondary endpoints will be analyzed sequentially in the order listed:

- Test first secondary endpoint at 0.05. If not significant, stop; otherwise,
- Test second secondary endpoint at 0.05. If not significant, stop; otherwise,
- Test third secondary endpoint at 0.05 using Hochberg (similar to the primary method). If not both IGA (0,1) and IGA 2 point reduction are significant, stop; otherwise,
- Test fourth secondary endpoint at 0.05 using the Hochberg method

For all efficacy analyses, small centers may be pooled in order to ensure sufficient cell counts for statistical testing.

Subgroup analyses (e.g. Gender, Age, Race, and Center) of the co-primary endpoints will be performed.

7.7.11 Interim Analysis

An interim analysis for futility will be conducted by an independent statistician. The sole purpose of the interim analysis is to help make a decision whether to continue the trial to the planned sample size, or to stop the trial for futility. No increase or decrease to the sample size will be performed, except to stop the trial for futility, therefore no adjustment to type-1 error is indicated. The interim analysis will be based on conditional power analysis when approximately 60 subjects (per group) have completed the double blind portion of the study. Only absolute lesion reduction count and IGA data (2 grade reduction, and Clear or Almost Clear (0, 1)) will be analyzed. The process for conducting the interim analysis and disseminating the recommendation to the sponsor will be described in the Statistical Analysis Plan. A charter will be written to describe in detail the process and roles related to this interim analysis. This charter will name the independent statistician to conduct the interim analysis, and the sponsor's designated personnel that will make final decisions.

7.7.12 Safety Analysis

Treatment emergent adverse events, and serious adverse events will be categorized by system organ class and Preferred Term from the current version of MedDRA. Treatment-emergent adverse events will be summarized overall, by severity, and by relationship to treatment. Changes from baseline in vital signs, laboratory parameters and shifts from baseline in laboratory parameters and physical examinations will be summarized by treatment. All safety endpoints will be displayed for all treated subjects. Safety analyses will be prepared for both the double-blind and open-label extension periods of the study, separately.

In addition, all safety data for omiganan treatment whether from the double-blind or open-label extension period of this study will contribute to the overall long-term safety database for omiganan which will be reported according to ICH-E1 and FDA guidance. Study subjects who were treated

CONFIDENTIAL

Version Date: 31 March 2017

with omiganan during the double-blind period and who continue into the open-label extension will be included in the planned 300 subjects to be exposed for 6 months and /or 100 subjects exposed for 1 year based on their duration of treatment.

7.7.13 Open Label Extension Summaries (Safety Extension Period: Week 16, 26, 39 and 52)

Summary statistics for the open-label extension study period will include baseline demographics, disposition, exposure, safety, and selected efficacy.

Efficacy summaries will include:

- The absolute change from baseline to Weeks 26 and 52 in inflammatory lesions (papules and pustules).
- IGA at Weeks 16, 26, 39, and 52: 2 point reduction; Clear or Almost Clear (IGA 0, 1).

Safety summaries will include:

- Concomitant medications
- Adverse events
- Vital signs, physical examinations, and laboratory tests at Week 52.

All efficacy and safety summaries will be performed by the original double blind randomized treatment group, and overall.

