In the open-label extension, subjects will apply omiganan topical gel. No concurrent rosacea therapy of any kind, especially over the counter antimicrobial soaps, prescription topical (on the face) and/or systemic antibacterial agents, will be allowed during the course of the study. No changes in topical soaps should occur. Other concurrent therapies will be recorded throughout the study. A bland non-medicated soap or soapless cleanser should be used for the purposes of washing, showering, and bathing. Safety assessments will be done on all of the designated study visit days. The end of the study will be the date that the last study subject completes the last visit for the study.

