- Remind the subject to contact the investigator if he/she experiences any adverse events.
- Remind the subject that the study medication tubes are not to be discarded and all must be returned to the site at the next study visit. Remind them to notify the site immediately if they have lost a tube.
- Remind the subject to apply the study drug once daily, as directed, preferably in the morning and record their daily treatment application in their diary.
- **The subject should apply the first dose of open label study drug the day after the Week 12 double blind study visit.**
- Remind the subject to return the diary to the site at the next study visit.
- Remind the subject to follow the treatment instructions.

7.3.2.5 Open-Label Extension Study Period Visits at Week 16, 26 and 39 (± 14 Days)

- Question the subject about any new or changes in adverse events.
- Question the subject about any new or changes in concomitant medications/therapies.
- Perform the Investigators Global Assessment (IGA) of rosacea (refer to Section 7.4.1). **Every effort should be made to maintain consistency of the evaluator for each subject.**
- Perform the inflammatory lesion count (papules and pustules) after completing the IGA assessment (refer to Section 7.4.4). **Every effort should be made to maintain consistency of the evaluator for each subject. It is important that the same evaluator performs the lesion counts for the same subject at each visit (Week 26 ONLY).**
- Obtain a blood sample for immunogenicity testing (Week 26 and Week 39 only)
- The subject should apply the study drug at the study site under supervision of the study coordinator or designee
- Treatment Compliance Check - Collect the study drug tubes and diary to perform a treatment application compliance review. Check compliance by reviewing the number of treatment applications in the diary to determine if there are missed doses. The subject should be re-instructed on study drug application, if compliance is an issue.
- Dispensing and Return of Study Treatment - Collect the used study medication tubes and weigh them. **Weigh and dispense 3 new tubes of omiganan topical gel.** Record the date of dispensing on the tube label. The dispensing and return information should be recorded on the source document. The subject should be reminded to completely use the gel in one tube before using another tube of gel.
- Collect the previous diary and dispense a new diary to the subject.

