#### **5.4.5 Safety Analysis**

Adverse events will be categorized by system organ class and Preferred Term from the current version of MedDRA. Treatment-emergent adverse events will be summarized overall and by seriousness, severity, and relationship to treatment using frequencies and percentages. Adverse events will be considered treatment-emergent if the onset date is on or after the first dose of study medication.

Changes from baseline in vital signs and laboratory parameters, and shifts from baseline in laboratory parameters will be summarized by treatment.

Safety summaries will be presented for the double-blind study period. Additional summaries will be presented for the open-label extension study period, based on the treatment received during the double-blind study period.

In addition, all safety data for omiganan treatment whether from the double-blind or open-label extension period of this study will contribute to the overall long-term safety database for omiganan which will be reported according to ICH-E1 and FDA guidance. Subjects who continue into the open-label extension study period will be included in the planned 300 subjects to be exposed for 6 months and 100 subjects exposed for one year based on their duration of omiganan treatment.

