#### **5.4.6 Open-Label Extension Summaries (Safety Extension Period: Week 16, 26, 39, and 52)**

Summary statistics for the open-label extension study period will include baseline demographics, disposition, exposure, safety, and efficacy variables.

Efficacy summaries will include:

- The absolute change from baseline to Weeks 26 and 52 in inflammatory lesions (papules and pustules).
- IGA at Weeks 16, 26, 39, and 52: 2 point reduction; Clear or Almost Clear (IGA 0, 1).

Safety summaries will include:

- concomitant medications
- adverse events that were emergent during the open-label extension study period
- vital signs and laboratory tests at Week 52.

All efficacy and safety summaries in the open-label extension study period will be performed by the original double blind randomized treatment group, and overall.

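### Emergence is dated by onset with no worsening criterion, so an adverse event that starts on vehicle and worsens on omiganan is probably missing from the extension table

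*Protocol*

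**What the plan says.** Every subject who continues past Week 12 receives active drug: "In the open-label extension, subjects will apply omiganan topical gel" (Protocol 7.1). Protocol 7.3.2.4 places the first open-label application on the day after the Week 12 visit. Safety is then reported by period: "Safety analyses will be prepared for both the double-blind and open-label extension periods of the study, separately" (Protocol 7.7.12).

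The protocol does not define treatment-emergence. SAP 5.4.5 does: "Adverse events will be considered treatment-emergent if the onset date is on or after the first dose of study medication". Among the extension safety summaries, SAP 5.4.6 lists "adverse events that were emergent during the open-label extension study period" and gives no further definition. The columns are set as follows: "All efficacy and safety summaries in the open-label extension study period will be performed by the original double blind randomized treatment group, and overall".

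On data collection, the instruction at the Week 12 visit and at the extension visits is the same: "Question the subject about any new or changes in adverse events". Protocol 7.5.6.1 asks for onset date, severity, relationship and outcome for each event. It does not say whether a later change in severity updates that entry or opens a new one. There is one exception. Protocol 7.4.2, 7.4.3 and 7.5.6.1 require worsening of erythema or of another rosacea sign or symptom to be recorded as an adverse event when the investigator attributes it to study drug.

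**The concern.** For a subject randomized to vehicle, the first dose of study medication is a vehicle dose. An event that begins on vehicle and worsens after omiganan is started has an onset date in the double-blind period. If onset alone decides the table, the worsening on omiganan is not shown in the extension table, although sites are told to ask about it.

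Safety is part of the primary objective, and long-term safety of omiganan is the secondary objective. The former-vehicle column of the extension table is where one would look for what happens when subjects start the drug, and omissions of this kind from it all favour omiganan. Few other planned summaries would show the worsening. The scales for erythema, telangiectasia, scaling and pruritus stop at Week 12 (Protocol 7.3.1). Apart from adverse events, the extension safety summaries are concomitant medications, and vital signs and laboratory tests at Week 52 (SAP 5.4.6).

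**Working it through.** The plan states no figure on this point, so the check is to apply the rule to an example and then show what range of counts could be involved.

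**Step 1: dates.** Day 1 is the first day of dosing (SAP 6.1). Week 12 falls at about 1 + 84 = Day 85, within ±3 days. The first open-label dose is the next day, about Day 86.

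**Step 2: one event, two ways of recording it.** A vehicle subject has a non-rosacea event with onset on Day 60, which becomes more severe on Day 100.

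- *Kept as one record, onset Day 60.* 60 ≥ 1, so it is treatment-emergent under SAP 5.4.5. 60 < 86, so it is not emergent in the extension if emergence there means onset on or after the first open-label dose. It appears only in the double-blind vehicle column.
- *Entered as a new record at worsening, onset Day 100.* 100 ≥ 86, so it is emergent in the extension and is counted there.

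The result depends on a recording convention that the documents do not give outside the rosacea signs and symptoms.

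**Step 3: can SAP 5.4.5 be used unchanged for the extension?** No. Measured from the first dose of study medication, the Day 60 and Day 100 records are both emergent, so the rule cannot separate the periods. SAP 5.4.6 needs its own reference date and does not state one. The natural adaptation is onset on or after the first open-label dose, which gives the exclusion in Step 2.

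**Step 4: who is affected.** In a subject on omiganan throughout, the Day 60 event is already in the omiganan column of the double-blind table. Only in subjects who move from vehicle to omiganan is the event credited to vehicle alone.

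**Step 5: illustrative size.** Number affected = 225 × share continuing × share with an event ongoing at the switch × share of those that worsen. The 225 is the planned vehicle arm. The shares are assumptions: 70–100%, 5–20% and 5–20%.

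- Low: 225 × 0.70 × 0.05 × 0.05 = 0.39
- Middle: 225 × 1.00 × 0.10 × 0.10 = 2.25
- High: 225 × 1.00 × 0.20 × 0.20 = 9.0

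These totals run across all event terms. They are also ceilings on what is lost, because any event re-entered as a new record would be counted.

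**The case against.** The strongest reply is that the exclusion is an inference. SAP 5.4.6 does not say that emergence means onset only, and Protocol 7.7.13 lists adverse events for the extension with no emergence restriction. Whether worsening opens a new line is normally settled in eCRF completion instructions, which are not among these documents. Other protections exist: drug-attributed worsening of rosacea signs, which matters most for a facial gel, must be recorded; clinically significant laboratory values are reported as adverse events (Protocol 7.5.3); and an event that becomes serious must be reported at once (Protocol 7.5.7). All of this stands, and it limits the point to what is probable. It does not remove the gap. Expedited reporting does not decide which table an event enters, and the rosacea exception leaves other events uncovered.

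A reader might also infer more than the documents support:

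- *That such worsening is never counted against omiganan.* The rosacea rule and any re-entered event show otherwise.
- *That each event has a single fixed severity.* Protocol 7.5.6.1 lists fields; it does not say how changes are stored. For the same reason, the documents do not show that severity reached on omiganan would overwrite a record in the vehicle column.
- *That Protocol 7.6.11 widens the gap,* because its prompt concerns new therapy "to treat any health condition/event not identified in" the medical history. That prompt adds a trigger and does not narrow the duty in 7.5.6.1 to report any adverse event. An event that began on vehicle would not ordinarily be in a history taken at Screening and updated at Baseline, so new therapy for it falls inside the trigger.
- *That undated events drop out,* because "In general, data will not be imputed for safety analysis" (Protocol 7.7.5). Onset date is required for every event, and eCRFs are checked for completeness.
- *That the randomized comparison is biased.* Worsening after the switch lies outside the double-blind period, and an event with onset on vehicle belongs in the vehicle column.

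**Conclusion.** The point holds in a limited form. The only stated emergence rule uses onset relative to the first dose of study medication, and emergence in the extension is not defined relative to the first omiganan dose. On the natural reading, a non-rosacea event that starts on vehicle, worsens or becomes serious on omiganan and is kept as one record is missing from the extension table and shown only under vehicle.

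The consequence is confined to descriptive open-label and long-term omiganan summaries. SAP 5.4.5 sends omiganan safety data from both periods to the long-term database but has no rule for an event that spans the switch. How that database attributes such events is not in these documents.

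The size cannot be established. The range of about 0.4 to 9 subjects rests wholly on assumed rates. Its upper end assumes that every planned vehicle subject continues, whereas Protocol 7.1 allows the extension to close before some subjects can enter it. Because the total is spread over many event terms, it should not be set against the incidence of any single reaction. The change is worth making because the stated objective is safety and the remedy is a few words.

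**What to change.** Make three changes before the extension data are tabulated.

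1. SAP 5.4.5: *An adverse event is treatment-emergent if its onset, or an increase in its severity or seriousness, occurs on or after the first dose of study medication.* This applies to both arms alike.
2. SAP 5.4.6: *An adverse event is open-label-emergent if its onset, or an increase in its severity or seriousness, occurs on or after the first open-label omiganan application.*
3. eCRF completion instructions: enter such an increase as a new adverse event line with its own start date, so that all sites record it the same way and both definitions can be applied from the data.

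The cost is two SAP sentences and one completion note. Visits, sample size and efficacy analyses do not change. Event counts rise slightly, and some events will appear in both periods. A footnote should say so, to keep readers from adding the two tables together.
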